- proportion of subjects with serious ADRs;
- severity of AEs;
- number of subjects who discontinued the study and the reasons for drop-outs;
- global assessment of tolerability by investigators: very good (no intolerance reactions), good (occasional intolerance reactions), moderate (frequent intolerance reactions), poor (intolerance reactions after every use);
- global assessment of tolerability by subjects: very good, good, moderate and poor

Clinical benefit assessment includes the following variables:

- global assessment of improvement by subjects score (0 to 4 scale: 0=much worse; 1= somewhat worse; 2=same; 3=somewhat improved; 4 = greatly improved)
- global assessment of improvement by investigators score (0 to 5 scale: 0 = worse; 1 = no appreciable improvement; 2 = slight improvement; 3 = moderate improvement; 4 = marked improvement; 5 = complete resolution)
- mean duration of primary treatment of disease (i.e., days with antibiotic use in case of infection or antiallergic medication in case of allergies),
- days with fever >38°C/days with symptoms,
- total and differential WBC count in blood and urine (if data are available).

Data sources

Data collection will be based on the review of medical records and routine examination of subjects. Regular medical records at study sites will serve as data sources.

Study size

Approximately 500 adult subjects

Data analysis

Descriptive and comparative statistical methods will be used.

A stratified analysis of main event of interest (i.e., adverse renal effect) will be performed by prior renal impairment and by use of concomitant nephrotoxic medicines to control confounders. Logistic regression will be employed to determine factors as possible predictors of adverse renal effect.

Stratified analysis by indication will be performed to investigate safety profile and clinical benefit in different subgroups of subjects.

Milestones

First eligible subject is planned to enrol on May 2016. Last subject last visit is expected to occur in November 2016.

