9.5. Study size

Due to the explorative character of the study and absence of the hypothesis to test, no formal attempt to calculate the sample size and power has been made.

A total of 500 subjects are expected to enter the study. It is assumed, that this number of subjects will allow to characterize the safety profile of Polyoxidonium and will be sufficient to identify, quantify and describe statistically the frequency of at least common ($\geq 1/100$, $< 1/10$) and uncommon ($\geq 1/1000$, $< 1/100$) adverse events and to allow for various subgroup analyses.

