9.7.1. Statistical methods

This study focuses primarily on the safety profile of Polyoxidonium and no statistical hypothesis testing is intended. Statistical analysis will be merely descriptive in nature.

Categorical data will be summarized in frequency tables. For continuous data, descriptive statistics (mean, median, minimum, maximum, standard deviation, 5% percentile, and 95% percentile) will be calculated. Comparative statistical analysis will be also performed. For statistical comparison of categorical data, the chi-square test will be used. Parametric Student t-test or nonparametric Wilcoxon rank sum test will be used for comparison of continuous data between two independent samples. Parametric paired Student t-test or nonparametric Wilcoxon signed-rank test will be used for comparison of continuous data between two dependent samples. Proportions of two dependent samples will be compared using McNemar's test. Statistical tests will be interpreted at the 5% significance level (two-sided).

A stratified analysis of main event of interest (i.e., adverse renal effect) will be performed by prior renal impairment and by use of concomitant nephrotoxic medicines to control confounders. Logistic regression will be employed to determine factors as possible predictors of adverse renal effects.

Stratified analysis by indication will be performed to investigate safety profile and clinical benefit in different subjects subgroups.

Data will be analyzed using SPSS software.

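### Protocol section 9.7.1 rules out hypothesis testing and then prescribes tests read at a two-sided 5% level; the two statements must be reconciled

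*Protocol*

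**What the plan says.** Section 9.7.1 opens by saying that "no statistical hypothesis testing is intended. Statistical analysis will be merely descriptive in nature". Later in the same section it says "Comparative statistical analysis will be also performed" and assigns a test to each type of data:

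- chi-square for categorical data;
- Student t or Wilcoxon rank sum for "comparison of continuous data between two independent samples";
- paired t or signed-rank for dependent continuous data;
- McNemar for dependent proportions.

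It then sets the reading rule: "Statistical tests will be interpreted at the 5% significance level (two-sided".

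Other sections line up on one side or the other. Section 9.5 gives the "absence of the hypothesis to test" as a reason for making no sample size or power calculation, and section 9.9 repeats that no hypothesis was formulated. The abstract (section 4) says "Descriptive and comparative statistical methods will be used".

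Three further statements matter. Section 9.1 calls the study exploratory but lists providing evidence that risks are absent among its purposes. Section 9.7 says the section supplies specifications for the SAP and that departures must be documented there. Section 9.7 also says that an analysis the data cannot support, for example because they are sparse, will not be done.

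**The concern.** A test interpreted at a significance level is a hypothesis test, whatever the section calls it. A SAP author who follows the first statement produces no tests. One who follows the second produces p-values with a 5% cut-off. Either author departs from the protocol.

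What is at stake is how a safety study is read. The study was not sized for any comparison, and nothing in the protocol says that p-values are only exploratory. A p-value under 5% in a subgroup may therefore be given more weight than it can bear. A p-value over 5% may be taken as the evidence of no risk that section 9.1 hopes for, although it may only reflect few events.

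A narrower point concerns the event of main interest. Section 9.7.1 stratifies adverse renal effects by prior renal impairment and by nephrotoxic co-medication. Chi-square is the only test it names for independent categorical groups. That approximation is weak when events are rare and one stratum is small.

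**Working it through.** **1. The plan's own figure.** The only figure is the two-sided 5% level per test. Section 9.5 says the 500 subjects rest on no calculation, so there is no power or sample size to reproduce.

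**2. The statements side by side.**

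| No testing | Testing |
|---|---|
| 9.7.1: "no statistical hypothesis testing is intended" | 9.7.1: "Comparative statistical analysis will be also performed" |
| 9.7.1: "Statistical analysis will be merely descriptive in nature" | 9.7.1: named tests read at 5%, two-sided |
| 9.5 and 9.9: no hypothesis | Abstract: "Descriptive and comparative statistical methods will be used" |

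No sentence reconciles the columns, for instance by calling the p-values exploratory.

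**3. What an unadjusted 5% rule can produce.** The number of tests k is not stated. Section 9.3.2 lists 9 safety variables and section 9.3.3 lists 5 benefit variables, so one test each gives k = 9 + 5 = 14. Assuming independent tests and all null hypotheses true, the chance of at least one false positive is 1 − 0.95^k, and the expected number is 0.05k.

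| k | Chance of at least one | Expected number |
|---|---|---|
| 5 | 1 − 0.95^5 = 22.6% | 0.25 |
| 14 | 1 − 0.95^14 = 51.2% | 0.70 |
| 70 (14 × 5 indications) | 1 − 0.95^70 = 97.2% | 3.5 |

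The k values of 5 and 70 are assumptions that bracket the case of 14. Analysing safety endpoints at each visit (section 9.7.2) could raise k. Correlation between endpoints would probably lower the chance of at least one false positive.

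**4. Chi-square with rare events in a small stratum.** Section 9.5 aims to describe uncommon events, from 1/1000 up to 1/100. In 500 subjects that is 500 × 0.001 = 0.5 to 500 × 0.01 = 5 expected events. Take 5 renal events, and assume that 3% of subjects (15 of 500) have prior renal impairment. Neither figure is in the protocol. The expected count in the small stratum is 5 × 15/500 = 0.15.

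Suppose one of the 5 events falls there. The table is 1 event and 14 non-events against 4 and 481. Pearson chi-square without continuity correction is

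500 × (1 × 481 − 14 × 4)² / (15 × 485 × 5 × 495) = 90,312,500 / 18,005,625 = 5.02, so p = 0.025.

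The chance that at least one of 5 events lands among those 15 subjects when there is no association is 1 − C(485,5)/C(500,5) = 14.2%. Fisher's exact p-value is the same 0.142. Here the nominal 5% rule would flag a pattern that chance produces about one time in seven.

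The result depends on the assumed stratum size and on the form of the test. With 10 subjects in the stratum p is 0.004 (Fisher 0.096); with 20 it is 0.067 (Fisher 0.185). With the continuity correction, the 15-subject case gives p = 0.36.

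**5. What an interval would show instead.** Clopper-Pearson 95% limits are 0.33% to 2.32% for 5 of 500, and 0.17% to 31.9% for 1 of 15. The second interval shows how little is known about the small stratum.

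**The case against.** The strongest reply is that the study is openly exploratory (sections 9.1 and 9.5), so a reader would treat its p-values as exploratory, and the conflict is loose wording. Multiplicity rules, exact tests and labels for p-values are also commonly left to the SAP. Part of this stands: the lack of a multiplicity method is not a finding by itself, and nothing in the protocol says that significant differences will be treated as findings. The contradiction remains, because both instructions are written into the section that specifies the SAP.

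Several stronger readings are tempting and should not be adopted:

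- **140 tests and 7 expected false positives.** A reader might multiply 14 variables by the 10 pairs of five indications. The safety variables are proportions, counts or ordered categories, and chi-square can compare five groups in one test. Only the 5 benefit variables could call for two-sample methods, which caps pairwise tests at 5 × 10 = 50. Even that is inferred: stratifying by indication can mean reporting within each stratum, and no text says indications are tested against each other.
- **The named methods do not fit the comparisons in general.** Paired tests suit the change in white cell count from baseline, and the two renal stratifiers can be treated as yes/no groups. What is missing is a test for more than two groups of continuous data, which matters only if indications are compared.
- **Chi-square always inflates false positives when data are sparse.** With 5 events over five equal strata of 100, p falls below 0.05 only if at least 4 events fall in one stratum, a chance of about 3%. The trouble lies in small, unbalanced strata.

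The sparse-data clause in section 9.7 is a partial answer. It lets an analysis be dropped, but it offers no exact alternative. If no renal event occurs, the question of which renal test to use does not arise.

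**Conclusion.** The contradiction is established from the text alone and needs no assumption. Its consequence is a risk of misreading in either direction; misuse is not shown.

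The 51% figure is an illustration resting on 14 independent tests with all nulls true. AEs, ADRs, SAEs and serious ADRs overlap, so the true figure is probably lower. Some benefit variables, such as duration of primary treatment, may differ between indications for real reasons, so a significant result there need not be false.

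The chi-square weakness is limited to rare events in small, unbalanced strata and rests on the assumed 5 events and 3% stratum.

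This should be corrected before database lock. It does not affect the data collected or the study's ability to estimate proportions, which is its primary aim.

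**What to change.** Preferred: delete the 5% interpretation sentence in section 9.7.1. Report each proportion with an exact (Clopper-Pearson) 95% confidence interval and each mean or median with a 95% confidence interval, overall and by stratum. Align the mention of comparative methods in section 9.7.1 and the abstract.

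If tests are kept:

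- remove the statements that no testing is intended and that the analysis is only descriptive;
- name the comparisons, and label p-values exploratory and unadjusted for multiplicity;
- use Fisher's exact test where expected counts are below 5;
- use one overall k-sample test, such as Kruskal-Wallis, if continuous variables are compared across indications;
- state that a non-significant result is not evidence of no risk.

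Either route changes wording in section 9.7.1, the abstract and the SAP. Visits, data collection and sample size stay as they are. The cost is giving up significance claims that the study was not sized to support.

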9. RESEARCH METHODS

9.1. Study design

This PASS is a local, multicentre, prospective, open-label, non-interventional, uncontrolled study.

Patients for whom Polyoxidonium is prescribed as a part of routine clinical practice will be eligible for this study. The decision to prescribe Polyoxidonium will be independent of the decision to enroll the subject into the study.

Primary treatment of a disease, Polyoxidonium administration, diagnostic procedures and assessments as well as visits schedule will be left at the discretion of investigators, according to local guidelines and routine clinical practices.

The study is explorative in nature. It is undertaken to systematically collect safety information in a community-based sample of subjects receiving Polyoxidonium therapy in routine care setting, to quantify potential risks, investigate potential risk factors and effect modifiers, or to provide evidence about the absence of risks.

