9.2.5. Study procedures

At the first visit, an investigator will inform a subject about the study (refer to Section 10.2.). If the subject consents to take part in the study and signs the written informed consent form, correspondent entry will be recorded in subject's medical records.

Then, a subject will be assigned a unique identification code, consisting of 4 symbols:

- number of the centre (2 digits),
- number of the subject in the center, by chronological order of selection (2 digits).

The investigator will maintain a subjects' identification list as part of the study file.

Actual assessments undertaken at each visit will be determined by clinical practice (see Study flow chart in Table 1). Subjects will not be administered any investigational medicinal products and/or medical procedures neither undergo any laboratory evaluations, diagnostic or monitoring procedures specifically for the purposes of this study.

Concomitant therapies will be administered at discretion of the investigator in accordance to routine clinical practice. According to the SmPC, Polyoxidonium may be administered as monotherapy or concomitantly with antibiotics, antivirals, antifungals, and antihistamines, bronchiolytics, corticosteroids, beta agonists, and cytostatic agents.

At the last visit (i.e., last injection visit), investigators and subjects will rate the overall tolerance of Polyoxidonium treatment as well as improvement.

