9.3.1. Definition of event of interest

In case of suspected adverse renal effect investigator will be encouraged to apply clinical judgement, to perform diagnostic workup and collect as much data as possible to confirm or reject the diagnosis of renal impairment. The signs and symptoms of renal toxicity, indicative of potential renal impairment include but are not limited to: increased blood concentrations of creatinine, potassium, blood urea nitrogen, urine protein levels, ECG changes, characteristic to elevated potassium levels; symptoms of intoxication, e.g. fatigue, nausea, vomiting.

These data for each subject for whom adverse renal effect is suspected will be reviewed and adjudicated by an independent assessor. This final adjudicated conclusion will be qualified as event of interest (a case of adverse renal effect) or suspicion about renal toxicity will be rejected.

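### The stratified and logistic analyses of renal cases cannot separate true renal risk from unequal detection, so an association with prior renal impairment could be created or inflated by closer surveillance

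*Protocol*

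**What the plan says.** **How a case arises.** Protocol Section 9.2.5 states that "Actual assessments undertaken at each visit will be determined by clinical practice" and rules out any laboratory or monitoring procedure done for the study. The footnotes to Table 1 (Section 9.2.4) confine laboratory tests and ECG to those done in routine care. Section 9.3.1 says: "In case of suspected adverse renal effect investigator will be encouraged to apply clinical judgement, to perform diagnostic workup". Only suspected subjects go to the independent assessor.

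**Who is analysed.** Section 9.7.2 takes every subject with at least one dose, whether or not any renal test was done.

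**What is done with case status.** Under Section 9.7.1 the stratified renal analysis "will be performed by prior renal impairment and by use of concomitant nephrotoxic medicines to control confounders". The next sentence reads: "Logistic regression will be employed to determine factors as possible predictors of adverse renal effects". The same section calls the analysis descriptive and disclaims hypothesis testing, but it also names comparative tests read at two-sided 5%. Section 9.1 says the study is meant "to quantify potential risks, investigate potential risk factors and effect modifiers, or to provide evidence about the absence of risks".

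**Size.** Section 9.5: "A total of 500 subjects are expected to enter the study", and "no formal attempt to calculate the sample size and power has been made".

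**The concern.** The outcome in these analyses is a detected renal case. Its observed frequency is the true risk multiplied by the chance that a case is noticed and worked up. Section 9.3.1 names creatinine, potassium, urea nitrogen and urine protein among the indicative signs, and none of these can be seen without a test. A history of renal impairment is an ordinary reason to order one, and a nephrotoxic drug may be.

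If so, the factor acts on detection as well as, or instead of, on risk. Stratifying by the factor or adjusting for it does not help, because the factor itself drives detection. Adjudication can reject false cases but cannot find missed ones.

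The study is part of a Risk Management Plan (Section 8). At stake is whether a subgroup is reported as being at higher renal risk when the difference may lie partly or wholly in how often its kidneys were checked.

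**Working it through.** **Plan's own figure.** There is none to reproduce. Section 9.5 gives 500 subjects without a calculation, and the protocol gives no renal event rate, exposure share or testing rate.

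**Inputs.** From the protocol: N = 500, two-sided 5%, chi-square test, all dosed subjects analysed. Assumed, with ranges shown: true risk r (equal in both strata), share of subjects with the factor, and detection probabilities d1 (factor present) and d0 (factor absent).

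**Apparent ratio when the true ratio is 1.**
- Observed risk in a stratum = r × d.
- Apparent risk ratio = (r × d1)/(r × d0) = d1/d0. Detection of 60% vs 30% gives 2, 90% vs 30% gives 3, and 80% vs 20% gives 4.
- Odds ratio at r = 3%, 80% vs 20%: observed risks are 0.024 and 0.006, so (0.024/0.976)/(0.006/0.994) = 4.07.

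The ratio does not depend on the number of cases.

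**Inflation of a real effect.** Take true risks of 4% vs 2% (odds ratio 2.04) and detection of 80% vs 20%. Observed risks are 0.032 and 0.004, giving (0.032/0.968)/(0.004/0.996) = 8.23.

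**False significance.** Cases in each stratum are binomial with probability r × d. The Pearson chi-square rejects above 3.841. The figures are exact sums over the two binomials, with 30% exposed (150 vs 350 subjects).

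| True risk | Equal, 30/30 | 60/30 | 90/30 | 80/20 | Expected observed cases (unequal detection) |
|---|---|---|---|---|---|
| 0.3% | 1% | 2% | 5% | 4% | 0.6–0.7 |
| 1% | 3% | 11% | 20% | 21% | 1.9–2.4 |
| 3% | 5% | 20% | 41% | 49% | 5.7–7.2 |
| 5% | 5% | 24% | 53% | 63% | 9.5–12.0 |

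Example of the last column, at 3% and 80/20: 150 × 0.024 + 350 × 0.006 = 3.6 + 2.1 = 5.7.

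- With 10% exposed and 3% risk, the rates run from about 14% (60/30) to 30% (80/20).
- With 80% exposed they are 1%, 5% and 3% at 3% risk, and 5%, 22% and 25% at 5% risk (60/30, 90/30, 80/20).
- Fisher's exact test is lower but still inflated: in simulation at 5% risk with 30% exposed, 16% for 60/30 and 55% for 80/20.

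**Would restricting to tested subjects cure it?** Suppose 3% true risk in both strata, routine testing of 80% vs 20%, and a suspicion-triggered test in half of the cases not routinely tested.
- Detection: 0.8 + 0.2 × 0.5 = 0.9 and 0.2 + 0.8 × 0.5 = 0.6. All-subject ratio = 0.9/0.6 = 1.50.
- Tested only, factor present: 0.03 × 0.9/(0.8 × 0.97 + 0.027) = 0.027/0.803 = 0.0336.
- Tested only, factor absent: 0.03 × 0.6/(0.2 × 0.97 + 0.018) = 0.018/0.212 = 0.0849.
- Tested-only ratio = 0.0336/0.0849 = 0.40.

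With a triggered share of 30% or 80%, the all-subject ratio is 1.95 or 1.14 and the tested-only ratio 0.51 or 0.31. The restriction turns an upward bias into a downward one.

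**The case against.** **No stated hypothesis.** Section 9.7.1 speaks only of possible predictors, does not list the regression covariates, and names the two factors as stratifiers to control confounding. Section 9.1 calls the study explorative. This stands, and no rule turns a significant factor into a conclusion. But the same text sets a 5% level, and Section 9.1 gives risk factors as an aim.

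**Low renal risk.** Sections 7.2 and 9.7 together weaken the size. No renal effects were reported in the clinical programme or in routine pharmacovigilance, with roughly 1,025,000 users estimated, and analyses may be dropped when data are sparse. At 0.3% there is no inflation above 5% with 30% exposed. At 1% about two cases would be observed, and the analysis might well be cancelled. That clause gives no protection once there are enough cases to run it.

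**Breadth of Annex 3.** The list includes penicillins, NSAIDs, proton pump inhibitors and H1 antagonists, so most subjects may count as exposed, and few of these drugs would prompt a kidney test. The concern is therefore weaker for co-medication than for prior renal impairment.

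**Existing safeguards.** Section 9.9 admits misclassification and information bias and announces a validation that would correct the estimates. Section 11.2 has every subject asked about adverse events at every visit, which evens out symptom reporting. Neither reaches laboratory signs in untested subjects. The validation is described without a reference standard or any sampling of unsuspected subjects, and Section 9.9 does not say that detection may depend on the factors being analysed.

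**Stronger readings.** A reader might infer that the analysis measures surveillance instead of harm, or that the bias worsens as cases accumulate. The documents support neither. Case status mixes the two, either factor may be a genuine risk factor, and only the rejection probability rises with case numbers.

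**Conclusion.** The point holds as a limit on interpretation. As fixed in Sections 9.3.1, 9.7.1 and 9.7.2, the renal comparison cannot separate risk from detection, and an association with prior renal impairment could be created or inflated. With equal true risk the apparent ratio is about the detection ratio, 2 to 4 in the scenarios shown. With 30% exposed and detection from 60/30 to 80/20, false significance is about 11–21% at 1% true risk and 20–49% at 3%, and at or below nominal at 0.3%.

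These figures rest on assumed risks, exposure shares and detection rates. That detection differs at all is a reasonable inference, not something the protocol states. A reader might also infer that the main analysis should be confined to tested subjects. That does not follow: where suspicion triggers tests the bias can reverse, and cases suspected from symptoms alone, which Section 9.3.1 allows, would be lost. This is a cheap improvement to make, not a defect that invalidates the study.

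**What to change.** In Protocol Section 9.7.1, carried into the SAP:

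1. Keep the all-subject stratified comparison and logistic regression as the main analysis.
2. Beside the case counts, show for each stratum the proportion of subjects with at least one on-treatment creatinine or urinalysis result, separating routine from suspicion-triggered tests where the record allows.
3. Add the analysis in tested subjects, preferably those routinely tested, as a sensitivity analysis only. Do not make persistence in that subset a condition for reporting a factor, since that could hide a real one.
4. State that where testing frequency differs materially between strata, an association is reported as possibly due to detection and is not interpreted as a risk factor.

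Laboratory results from routine care are already entered in the eCRF (Section 9.3), so no procedure is added and the study stays non-interventional. The cost is a little more tabulation and a more cautious predictor conclusion.
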